1 PROTOCOL SUMMARY

1.1 SYNOPSIS

Title:	A Phase II Study of Fostamatinib to Treat Post-transplant Immune-mediated Cytopenias
Study Description:	This open label phase II trial is designed to evaluate the efficacy of fostamatinib in the treatment of post-transplant cytopenias as assessed by hematologic improvement in anemia and/or thrombocytopenia following a 12-week treatment course. Patients who respond to the 12-week treatment course on this single arm study are eligible and have the option to enroll on the extended access trial.
Objectives:	
The primary objective is to assess efficacy of fostamatinib for stable hematologic recovery during post-hematopoietic stem cell transplant immune mediated anemia and/or thrombocytopenia.
 
The secondary objective is to assess efficacy of fostamatinib for clinically-relevant outcomes in post-hematopoietic stem cell transplant patients.
 
The exploratory objective is to evaluate changes in serologic markers that may be associated with cytopenias while on treatment to identify key elements for fostamatinib response.

Endpoints:	
Primary endpoints:
 
The proportion of subjects with hematologic recovery that is stable, defined as improvement documented in 2 consecutive available readings at least 2 weeks apart, without recent blood product transfusion support in the past 7 days.
 
Hematologic recovery is defined as:
 
 • Hemoglobin ≥ 10 g/dL (or at least ≥ 2 g/dL above baseline) in subjects enrolled with posttransplant anemia. In subjects with symptomatic anemia, a hemoglobin increase of at least ≥ 2 g/dL above baseline is required 
OR
 
 • Platelets $\geq 50 \times 10^9/L$ (or at least $\geq 20 \times 10^9/L$ above baseline) in subjects enrolled with posttransplant thrombocytopenia 
OR
 
 • Both of the above criteria in subjects with posttransplant Evans syndrome 
Secondary endpoints:
 
 1. Proportion of subjects who achieve objective hematologic recovery within the 12-week treatment course defined as:

Abbreviated Title: Fostamatinib for post-transplant cytopenias

Version Date: 11/28/2023

	
 • Hemoglobin ≥ 9 g/dL (or at least ≥ 1 g/dL above baseline) in subjects enrolled with anemia or at least ≥ 1 g/dL above baseline in subjects with symptomatic anemia 
OR
 
 • Platelets $\geq 30 \times 10^9/L$ (or at least $\geq 10 \times 10^9/L$ above baseline) in subjects enrolled with thrombocytopenia 
OR
 
 • Either of the above criteria in subjects with Evans syndrome 
 2. Average weekly requirement of transfused blood component or growth factor requirement (total units of PRBC or Platelets/week, total dose of growth factor/week) by week 12, compared to the week prior to the start of the study drug. 3. Change in corticosteroid dose over time, measured by median daily weight-based prednisone-equivalent corticosteroid dose in a week, from week 1 to week 12 4. Change in other immunosuppressant dose over time, measured by median daily dose of the immunosuppressant in a week, from week 1 to week 12 5. Number of patients who achieved $\geq 50\%$ steroid dose reduction by week 12 compared to week 1 6. Incidence and severity of cGVHD according to 2014 NIH Consensus Criteria, at baseline before the initiation of treatment, and at week 12 
Exploratory endpoints:
 
 1. Absolute percentage change in B cell chimerism pre-treatment, vs weeks 4 and 12. 2. cPRA change in the preformed HLA antibodies before and after treatment in subjects with thrombocytopenia or Evans syndrome 3. Percent MFI change of preformed HLA antibodies before and after treatment. This applies for antibodies with an MFI $>1,000$. 4. Anti-RBC alloantibody titer change in patients with hemolytic anemia before and after treatment 5. Assessment of serial cytokines pre-treatment and weeks 4 and 12. Cytokines include CRP, IL-1, IL-2, IL-6, IFNγ, TNFα, EPO and TPO 6. Immunoglobulin level changes pre-treatment, and weeks 4 and 12. 7. Absolute reticulocyte count, lactate dehydrogenase, haptoglobin changes pre-treatment, and at each biweekly study visit, in patients with anemia or Evans syndrome 8. Change in the weekly rate and severity of bleeding according to the total score of the ITP-Bleeding Scale (IBLS), from week -1 (one week before the start of the study drug) to week 12, in subjects with thrombocytopenia or Evans syndrome
Study Population:	This trial is intended to include adult patients with post hematopoietic stem cell transplant immune-mediated anemia, thrombocytopenia, or both (Evans syndrome) evaluated on or after day 60 post transplantation.
Phase:	Phase II

Abbreviated Title: Fostamatinib for post-transplant cytopenias

[figure not shown]
Version Date: 11/28/2023

Description of Sites/Facilities Enrolling Participants:	This will be a multi-center study. Enrollment will take place at the NIH Clinical Center and at up to three additional participating sites. We will enroll a total of 20 patients. The study will be conducted exclusively in the United States. Data Coordinating Center (DCC): National Heart, Lung and Blood Institute (NHLBI)
Description of Study Intervention:	The study intervention is fostamatinib, an inhibitor of spleen tyrosine kinase that will be prescribed orally at a dose of 100 mg twice daily for 4 weeks followed by a hematological response assessment. On the week 4 evaluation visit, a) if cytopenias improve (hemoglobin \geq 10 g/dL, platelets \geq 50 x 10 ⁹ /L), patients will continue the same dose for a total of 12 weeks, b) if refractory cytopenias persist (hemoglobin $<$ 10 g/dL, platelets $<$ 50 x 10 ⁹ /L), fostamatinib dose will be increased to 150 mg BID. The duration of the study is 12 weeks with the option to enrol patients who respond on an extended access trial
Study Duration:	This study will enroll over 48 months followed by an additional 4months for data analysis
Participant Duration:	An individual subject will complete the study in 15 weeks, from screening at week -1 or 0 to follow-up on week 14 \pm 3 days.

Abbreviated Title: Fostamatinib for post-transplant cytopenias

Version Date: 11/28/2023

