1.3 SCHEDULE OF ACTIVITIES (SOA)

Study Week ^k	-1	0	2 ^d	4 ^d	6 ^d	8 ^d	10 ^d	12 ^d	14 ^{e,f} (end of study safety visit)
Informed Consent	X ^b	X ^b							
Inclusion/exclusion	X ^b	X ^b							
Pregnancy Test	X ^b	X ^b		X		X		X	
HIV, HBV, HCV testing	X ^{b,j}	X ^{b,j}							
Medical History	X ^b	X ^b							
Medical assessment ^a	X	X	X	X	X	X	X	X	X
Physical Exam	X ^b	X ^b							
Follow up and labs ^{c,d} : CBC, BMP, LFTs, LDH, absolute reticulocyte count, haptoglobin, stool occult blood, urinalysis	X ^b	X ^b	X	X	X	X	X	X	X
Study drug (fostamatinib) administration ^g		X	X	X	X	X	X		
B-cell chimerism and Cytokines ^h		X ^b		X		X		X	
IBLS [1] ⁱ	X ^b	X ^b	X	X	X	X	X	X	
cPRA, MFI, immunoglobulin level, RBC antibody		X		X		X		X	

- a) Vital signs, transfusion support evaluation, concomitant medication review and steroids taper assessment
- b) Can be done within 7 days before or at time of enrollment
- c) Follow up visits will be completed as outpatient in-person visits at the NIH Clinical Center, or via telehealth/telephone if patients are unable to travel for any reason (except for weeks 4 and 12 where patients are required to return to the NIH Clinical Center). Labs can be completed locally, and results will be provided to the research team.
- d) Can be performed +/- 4 days from scheduled visit.
- e) Outpatient visit can be +/- 3 days from scheduled visit.
- f) Patients who rolled over to 000760-H will not need to return for week 14 visit, they will transition all study follow up to 000760-H. The patients who do not roll over will complete their week 14 safety visit on 000758-H.

Abbreviated Title: Fostamatinib for post-transplant cytopenias

Version Date: 11/28/2023

- g) Study drug will be mailed from Rigel or the clinical center pharmacy and be distributed to the research subjects from the pharmacy directly to the research subjects. The pill count will be reviewed every 2 weeks at the medical assessment visit.
- h) Including CRP, IL-1, IL-2, IL-6, IFN γ , TNF α , EPO and TPO
- i) See Appendix B
- j) Within 6 months

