3 STUDY DESIGN

3.1 OVERALL DESIGN

Our plan is to study fostamatinib for the treatment of immune-mediated posttransplant cytopenias (anemia, thrombocytopenia or both)

- This will be a multicenter, open label, phase II study, with no control arm with the primary objective to test the efficacy of fostamatinib in the treatment of posttransplant cytopenias.
- All study participants will receive fostamatinib 100 mg BID for 4 weeks. On the 4-week evaluation, a) if the cytopenia improves (hemoglobin ≥ 10 g/dL, platelets $\geq 50 \times 10^9/L$), patients will continue the same dose for a total of 12 weeks b) if refractory cytopenias persist (hemoglobin < 10 g/dL, platelets $< 50 \times 10^9/L$), subjects will increase dose to 150mg BID. Subjects with persistent (≥ 2 readings, 2 weeks apart) loss of hematologic response after week 5 can increase the study drug dose to 150mg BID until they are at the end of the study on week 12.
- This trial will be done primarily in an outpatient setting. Follow up visits will be completed as outpatient in-person visits at the participating site or via telehealth or telephone if patients are unable to travel for any reason, with labs drawn by local providers in this circumstance.
- The 4-week assessment is the first milestone where dose can be adjusted if necessary. At the end of the trial, participants with objective hematologic recovery will be given the option to enroll onto an extended access trial, including:
 - Post-transplant anemia who achieved a hemoglobin ≥ 9 g/dL (or 1 g/dL above baseline) without transfusion support, at least once in the 12-week phase II study period

Abbreviated Title: Fostamatinib for post-transplant cytopenias

Version Date: 11/28/2023

- Post-transplant thrombocytopenia who achieved a platelet count $\geq 30 \times 10^9/L$ (or $10 \times 10^9/L$ above baseline), without transfusion support, at least once in the 12-week phase II study period
 - Either of the above in subjects with Evans syndrome
- The plan is to treat and include a total of 20 patients in the analysis in this single arm trial.

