4 OBJECTIVES AND ENDPOINTS

OBJECTIVES	ENDPOINTS	JUSTIFICATION FOR ENDPOINTS
Primary		
Efficacy of fostamatinib for stable hematologic recovery during post-hematopoietic stem cell transplant immune mediated anemia and/or thrombocytopenia.	
 • The proportion of subjects with hematologic recovery that is stable, defined as improvement documented in 2 consecutive available readings at least 2 weeks apart, without recent blood product transfusion support in the past 7 days. 
Hematologic recovery is defined as:
 
 • Hemoglobin ≥ 10 g/dL (or at least ≥ 2 g/dL above 	The endpoints are all clinically relevant to answer the trial hypothesis and indicative of clinical recovery. The endpoints were chosen to be similar to the previous FIT trials that led to FDA approval of fostamatinib in chronic ITP.

Abbreviated Title: Fostamatinib for post-transplant cytopenias

Version Date: 11/28/2023

	
baseline^{&}) in subjects with posttransplant anemia. In subjects with symptomatic anemia*, a hemoglobin increase of at least ≥ 2 g/dL above baseline is required
 
OR
 
 • Platelets $\geq 50 \times 10^9/L$ (or at least $\geq 20 \times 10^9/L$ above baseline) in subjects with posttransplant thrombocytopenia 
OR
 
 • Both of the above criteria in subjects with posttransplant Evans syndrome 	
Secondary		

Efficacy of fostamatinib for clinically-relevant outcomes in post-hematopoietic stem cell transplant patients
	
1. Proportion of subjects who achieve objective hematologic recovery within the 12-week treatment course defined as:
 
 • Hemoglobin ≥ 9 g/dL (or at least ≥ 1 g/dL above baseline) in subjects enrolled with anemia or at least ≥ 1 g/dL above baseline in subjects with symptomatic anemia 
OR
 
 • Platelets $\geq 30 \times 10^9/L$ (or at least $\geq 10 \times 10^9/L$ above baseline) in subjects enrolled with thrombocytopenia 
OR
 
 • Either of the above criteria in subjects with Evans syndrome 
2. Average weekly requirement of transfused blood component or growth factor requirement (total units of PRBC or Platelets/week, total dose of growth factor/week)
	
The secondary endpoints are all relevant to safety of fostamatinib for post-hematopoietic stem cell transplant setting

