9 STATISTICAL CONSIDERATIONS

9.1 STATISTICAL HYPOTHESIS AND SAMPLE SIZE DETERMINATION

This study will use a Simon two-stage minimax design [23] to test the null hypothesis (H_0) that the response rate after 12 week (primary endpoint defined in Section 3) is $\leq 10\%$ versus a one-side alternative. If the true response rate, meaning the rate of meeting the primary endpoint at 12 weeks, is 35%, the following two-stage design would have a power of 86% with a type 1 error of 0.05.

In the first stage, the study will enroll 11 subject. If ≤ 1 subjects achieve a response, the study will stop for futility and H_0 is not rejected. If 2 or more subjects achieve a response, the study will proceed to the second stage and enroll an additional 9 subjects for a total of 20 evaluable subjects. The H_0 will be rejected, meaning that the study is not futile, if more than 4 responses are observed in 20 subjects.

Subjects who discontinue treatment before completing 4 weeks, with discontinuation being unrelated to the treatment-related adverse event or disease progression will not be evaluated for the primary endpoint. Early discontinuation within 12 weeks due to toxicity or AE related to the study drugs or disease progression is counted as non-response towards the primary endpoint and these subjects will not be replaced. Safety will be assessed in subjects who received at least one dose of fostamatinib. Up to 8 additional subjects may be enrolled to account for treatment discontinuations before completing 4 weeks for reasons unrelated to treatment or disease progression. Early discontinuation within 12 weeks due to toxicity or AE related to the study drugs is counted as non-response towards the primary endpoint and these subjects will not be replaced.

Abbreviated Title: Fostamatinib for post-transplant cytopenias

Version Date: 11/28/2023

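### The two-week spacing in the primary endpoint is missing from Section 9.3.2 and does not fit the ±4-day visit windows, so a compliant late responder can be scored a non-responder

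*Combined protocol and SAP*

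**What the plan says.** Section 1.1 defines stable recovery as "improvement documented in 2 consecutive available readings at least 2 weeks apart, without recent blood product transfusion support in the past 7 days". The table in Section 4 has the same spacing: "2 consecutive available readings at least 2 weeks apart". Section 9.3.2, which governs the primary analysis, mentions two consecutive readings and the 7-day transfusion clause but gives no minimum spacing. It refers the reader to Section 3. That section is Study Design and does not contain the primary endpoint, which is in Section 4. Sections 9.1, 9.2.1 and 9.3.3 carry the same pointer.

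Blood counts from week 2 to week 12 are due every two weeks (Sections 1.3 and 8.2.2). Footnote d of Section 1.3 allows a window: "Can be performed +/- 4 days from scheduled visit".

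On timing, Section 9.1 refers to the response rate after 12 weeks and explains the 35% as "the rate of meeting the primary endpoint at 12 weeks". It does not say which visits may form the pair. Two neighbouring rules are more explicit. Secondary endpoint 1 is the "Proportion of subjects who achieve objective hematologic recovery within the 12-week treatment course", and the rollover rule in Section 3.1 asks for recovery "at least once in the 12-week phase II study period". Section 1.3 labels week 14 the "end of study safety visit", and footnote f adds: "Patients who rolled over to 000760-H will not need to return for week 14 visit".

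**The concern.** The spacing rule equals the nominal visit interval, so it leaves no tolerance, while the schedule allows four days either way. Whenever the second visit of a pair falls earlier in its window than the first did, the gap is under 14 days. A patient who recovers early has further pairs to qualify on. A patient first positive at week 10 has only the week-10/12 pair.

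The open question on timing matters too. A patient who meets the criterion at weeks 4 and 6 and then loses it is a responder if any pair up to week 12 counts, and a non-responder if the pair must be present at week 12. Section 6.1.2.1 makes provision for loss of response, so the plan expects such patients.

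The trial has one open-label arm and small counts. It stops at 1 or fewer responders of 11 and rejects the null hypothesis at more than 4 of 20. Moving one patient from 2 to 1 at the first stage, or from 5 to 4 at the end, reverses the decision. A scoring rule settled after the data are seen would be hard to defend.

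**Working it through.** **Inputs from the documents.** Section 9.1: null rate 0.10, alternative 0.35, n1 = 11, stop at 1 or fewer, n = 20, reject at more than 4, stated power 86%, type I error 0.05. Section 1.3: visits 14 days apart, ±4 days. Sections 1.1 and 4: gap of at least 14 days.

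**1. The plan's own figure.** P(reject) = Σ over x = 2 to 11 of Bin(x; 11, p) × P(Bin(9, p) ≥ max(0, 5 − x)).
- p = 0.35: 0.860, which reproduces the stated 86%.
- p = 0.10: 0.040, under the 0.05 limit.

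**2. The gap.** Let d1 and d2 be the offsets of two adjacent visits, each from −4 to +4. Gap = 14 + d2 − d1, with a minimum of 14 − 8 = 6 and a maximum of 14 + 8 = 22 days. For weeks 10 and 12 these are days 66 to 74 and 80 to 88. There are 9 × 9 = 81 day combinations. In 9 of them the gap is exactly 14 days, and by symmetry (81 − 9)/2 = 36 fall short: 36/81 = 44%. This counts combinations; it is not an observed rate.

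**3. Chance that a week-10 responder is missed.** The documents do not give the distribution of visit days. Assume independent offsets with the same distribution at each visit, so that P(short) = (1 − P(d1 = d2))/2.

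| Assumed timing | P(d1 = d2) | P(short) |
|---|---|---|
| Uniform over the 9 days | 1/9 = 0.111 | 0.444 |
| Triangular, peak on the day | 85/625 = 0.136 | 0.432 |
| 50% on the day, rest even | 0.25 + 8 × 0.0625² = 0.281 | 0.359 |
| 80% on the day, rest even | 0.64 + 8 × 0.025² = 0.645 | 0.178 |
| Each visit at least 14 days after the last | not applicable | 0 |

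The effect is concentrated in late responders. If each adjacent pair must itself span 14 days, a patient first positive at week 8 is missed in 1.5% to 11.5% of cases. If the week-8 and week-12 readings may be paired, the figure is 0%.

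**4. Illustration of the effect on power.** This applies only if 35% meant recovery at two adjacent scheduled visits. Let m be the assumed share of responders first positive at week 10. Counted rate = 0.35 × (1 − m × P(short)).
- m = 0.10, uniform: 0.35 × (1 − 0.0444) = 0.334, power 0.827. With 80% on the day: 0.344, power 0.848.
- m = 0.20, uniform: 0.35 × (1 − 0.0889) = 0.319, power 0.789. With 80% on the day: 0.338, power 0.834.
- Adding the week-8 loss, with the same share m first positive at week 8, widens the overall range to 0.767 to 0.848.
- Week-10 responders lost per 20 patients = 20 × 0.35 × m × P(short): from 7 × 0.10 × 0.178 = 0.12 to 7 × 0.20 × 0.444 = 0.62.

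**5. Can the windows accommodate the 14-day rule?** A visit at offset d, followed exactly 14 days later, falls at offset d of the next window. Since d is at most 4, that day is always inside the window. If one visit is missed, the gap across it is 28 ± 8 days, at least 20, so that pair still qualifies.

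**The case against.** The strongest reply is that Section 9.3.2 is shorthand. It uses the word stable, which Sections 1.1 and 4 define with the spacing, and it sends the reader elsewhere for the endpoint. This largely stands. A reader might infer that the plan holds two rival primary endpoints, but there is only one full definition, and 9.3.2 is most naturally an abridgement of it. What remains is that the analysis section omits a decisive element and its cross-reference does not supply it.

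A reader might also infer that the endpoint has no period at all, or that week 14 could supply the confirming reading. The documents do not support this. Section 9.1 ties the endpoint to 12 weeks twice, and week 14 is a safety visit that rollover patients skip. Only the choice between any pair by week 12 and a pair present at week 12 is open.

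A third tempting inference is that the trial is underpowered. Section 9.1 defines 35% as the rate on the primary endpoint itself, so the 86% is right as written. The lower figures in step 4 need a different meaning of 35%, assumed visit timing and assumed shares of late responders.

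Finally, the endpoint speaks of available readings, and counts may be drawn locally. The plan does not say whether unscheduled counts qualify. If they do, some late responders could be rescued, so the 18% to 44% also assumes that only scheduled readings are available.

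**Conclusion.** The point holds as a gap in the definition of the primary endpoint that should be fixed. It is not an error in the sample size. The following rests on the documents and arithmetic alone: the spacing is absent from 9.3.2, the pointers to Section 3 are wrong, compliant adjacent visits can be 6 to 22 days apart, gaps of 6 to 13 days fail, and Section 9.1 does not say how the 12-week limit applies to the pair. If only scheduled readings are available, a sustained responder first positive at week 10 can be counted as a failure without any deviation.

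The size is less certain. The 18% to 44% miss rate among such patients depends on assumed visit timing and is 0% if visits are kept at least 14 days apart. The expected loss is under one responder per 20 patients in every scenario shown. The power figures are illustrations. The practical weight comes from the decision limits, where a single patient can decide the result.

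**What to change.** Use one definition in Sections 1.1, 4, 9.1 and 9.3.2:
- Restore the minimum of two weeks between readings in 9.3.2.
- Correct the pointer from Section 3 to Section 4 in 9.1, 9.2.1, 9.3.2 and 9.3.3.
- In 9.1, replace both 12-week phrases with wording that the pair must be complete by the week-12 visit or, if that is what is meant, that it must be present at week 12.
- State that week-14 readings do not count, and whether unscheduled readings may form part of a pair.
- Add to footnote d of Section 1.3 that each response blood count from week 2 to week 12 is drawn at least 14 days after the previous scheduled one.

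No compliant pair of scheduled readings then fails on spacing. The endpoint is not loosened, so the design's error rates are unchanged. The cost is slightly less scheduling flexibility: after a late visit, the next one cannot move earlier within its window. No visits or data are added.

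An alternative is to define the pair as two consecutive scheduled visits, with the window tolerance applied to the spacing. This suits only if the sponsor confirms that the 10% and 35% rates refer to that definition. It admits pairs 6 to 13 days apart. If 10% was set for the 14-day rule, the null rate on the looser definition may be higher. Type I error stays at or below 0.05 only while that rate is at most about 10.6%; at 12% it would be 0.076. In that case the alternative should not be adopted without restating the operating characteristics.

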	
by week 12, compared to the week prior to the start of the study drug.
 
 3. Change in corticosteroid dose over time, measured by median daily weight-based prednisone-equivalent corticosteroid dose in a week, from week 1 to week 12 4. Change in other immunosuppressant dose over time, measured by median daily dose of the immunosuppressant in a week, from week 1 to week 12 5. Number of patients who achieved $\geq 50\%$ steroid dose reduction by week 12 compared to week 1 6. Incidence and severity of cGVHD according to 2014 NIH Consensus Criteria, at baseline before the initiation of treatment, and at week 12 	
Tertiary/Exploratory		
The exploratory objective is to evaluate changes in serologic marker while on treatment to identify key biological pathways impacted by fostamatinib that may lead to a response to therapy	
 1. Absolute percentage change in B cell chimerism pre-treatment, vs weeks 4 and 12. 2. cPRA change in the preformed HLA antibodies before and after treatment in subjects with thrombocytopenia or Evans syndrome 3. Percent MFI change of preformed HLA antibodies before and after treatment. This applies for antibodies with an MFI $>1,000$. 4. Anti-RBC alloantibody titer change in patients with hemolytic anemia before and after treatment 5. Assessment of serial cytokines pre-treatment and weeks 4 and 12. Cytokines include CRP, IL-1, IL-2, IL-6, IFNγ, TNFα, EPO and TPO 6. Immunoglobulin level changes pre-treatment, and weeks 4 and 12. 	These exploratory endpoints are relevant to the ex vivo and in vitro analysis that will help predict response and define mechanisms of action of fostamatinib for resolving cytopenias

	
7. Absolute reticulocyte count, lactate dehydrogenase, haptoglobin changes pre-treatment, and at each biweekly study visit, in patients with anemia or Evans syndrome
 
8. Change in the weekly rate and severity of bleeding according to the total score of the IBLS, from week -1 (one week before the start of the study drug) to week 12, in subjects with thrombocytopenia or Evans syndrome[#]
	
--	--	--

&: Baseline is defined as the mean of the last two hemoglobin or platelet measured at least 24 hours apart, at least 72 hours from the last transfusion, within 14 days of the start of the study drug

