5.1 INCLUSION CRITERIA

- Ages 18-75 years inclusive
- Ability to comprehend the investigational nature of the study and provide informed consent
- Female patients of reproductive potential agree to avoid pregnancy through abstinence or the use of two forms of highly effective birth control during and for 1 month after the last study treatment and agree not to donate eggs during this time
- Male patients of reproductive potential agree to avoid pregnancy of a partner through abstinence or the use of two forms of highly effective birth control during and for 1 month after the last study treatment and agree not to donate sperm during this time.
- Diagnosis of an immune mediated cytopenia (anemia and/or thrombocytopenia)[‡] in a patient that either:
 - Failed or relapsed after at least one line of therapy including steroids, IVIG, TPO mimetics, rituximab, azathioprine, cyclophosphamide, cyclosporine, tacrolimus, danazol, vincristine, ESA or splenectomy
 - Or remains transfusion dependent (≥ 1 transfusion(s)/2 weeks)
 - Or is steroid dependent*
- Subjects are ≥ 60 days post-allogeneic transplant with:
 - Thrombocytopenia, defined as average platelets count $< 30 \times 10^9/L$ for 3 consecutive available readings at least 2 weeks apart, after other cell lines have engrafted, with no counts $> 40 \times 10^9/L$ unless from rescue transfusions. Subjects failed at least one line of therapy outlined above with a clinical diagnosis of immune mediated thrombocytopenia.

- Anemia, transfusion dependent, or defined as hemoglobin ≤ 9 g/dL for 3 consecutive available readings at least 2 weeks apart, after other cell lines have engrafted OR if hemoglobin 9-10 g/dL, subject must have symptomatic anemia or ongoing treatment for immune hemolytic anemia that have failed at least one line of therapy outlined above. Symptomatic anemia is defined as anemia with fatigue, weakness, shortness of breath, palpitations/fast heartbeat, lightheadedness, and/or chest pain, and these symptoms are attributed to anemia. Laboratory evaluation are recommended but not required for the diagnosis, such as a positive DAT, low haptoglobin $<$ lower limit of normal (LLN), indirect bilirubin $>$ upper limit of normal (ULN), or lactate dehydrogenase (LDH) $>$ ULN.
- Subjects must test negative for HIV, HBV, and HCV by standard serologic tests within the previous six months

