6.6 TRANSFUSIONS

During the study period, packed RBC transfusion should be administered when hemoglobin <7g/dL, or <9g/dL with symptoms; platelet transfusion should be administered when platelet count <10g/dL. Additional transfusions may be administer per the discretion of the PI or the local HCT provider. The number of units transfused should be documented.

Transfusions between scheduled study visits can be done locally or at the sites per institutional standards.

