9.3.2 Analysis of the Primary Endpoints

The primary endpoint (see Section 3) is the proportion of subjects with stable hematologic recovery (2 consecutive readings) without recent blood product transfusion support (in the past 7 days).

Hematologic recovery is defined as:

Hemoglobin ≥ 10 g/dL (or at least ≥ 2 g/dL above baseline) in subjects with posttransplant anemia. In subjects with symptomatic anemia, a hemoglobin increase of at least ≥ 2 g/dL above baseline is required

OR

Platelets $\geq 50 \times 10^9/L$ (or at least $\geq 20 \times 10^9/L$ above baseline) in subjects with posttransplant thrombocytopenia

OR

Both of the above criteria in subjects with posttransplant Evans syndrome

The proportion of people who meet the above response criteria will be estimated using sample proportions, and their inferences including confidence intervals and hypothesis testing will be evaluated using binomial distributions.

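### The primary endpoint does not require the interval between its two readings to be transfusion-free, so a subject who is still transfusion dependent can meet the transfusion clause

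*Combined protocol and SAP*

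**What the plan says.** The Synopsis (1.1) and Section 4 define stable recovery as improvement in "2 consecutive available readings at least 2 weeks apart, without recent blood product transfusion support in the past 7 days". Section 9.3.2 restates it as "stable hematologic recovery (2 consecutive readings) without recent blood product transfusion support (in the past 7 days"), without the 2-week spacing. None of the three places says whether the 7 days apply at each reading or only once, or what happens if a transfusion falls between the readings.

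The count criteria are hemoglobin of at least 10 g/dL or a rise of at least 2 g/dL (for symptomatic anemia, the rise is required), platelets of at least 50 x 10^9/L or a rise of at least 20 x 10^9/L, and both lineages for Evans syndrome.

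Section 5.1 admits a subject who "Or remains transfusion dependent", with dependence set at one or more "transfusion(s)/2 weeks". The anemia criterion, "Anemia, transfusion dependent, or defined as hemoglobin", puts no hemoglobin ceiling on the transfusion-dependent route.

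Section 6.6 gives red-cell triggers of hemoglobin below 7 g/dL, or below 9 g/dL with symptoms, and adds: "Additional transfusions may be administer per the discretion of the PI or the local HCT provider". It asks for the number of units to be documented. Baseline (Section 4) uses counts taken "at least 72 hours from the last transfusion, within 14 days of the start of the study drug".

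**The concern.** The entry definition works on a 2-week scale and the response definition looks back 1 week. A subject can therefore be transfused at the rate that defines dependence and still have a clean 7 days before each qualifying reading. If donor cells help hold the count up at both readings, carry-over from transfusion is scored as stable recovery on fostamatinib.

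The trial is single-arm and open-label, so there is no control group in which such carry-over would cancel. The decision rule turns on single subjects: 2 responses in 11 to continue and 5 in 20 to reject H0. Secondary endpoint 2 (average weekly transfusion requirement) would describe continuing need, but it does not reclassify a responder.

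**Working it through.** **Design figures (Section 9.1).** Stage 1: 11 subjects, stop at 1 or fewer responses. Total: 20 subjects, reject H0 at 5 or more. The chance of rejection is the sum over x = 2 to 11 of P(X1 = x | 11, p) × P(X2 ≥ 5 − x | 9, p).

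- p = 0.35: 0.1395 × 0.6627 + 0.2254 × 0.8789 + 0.2428 × 0.9793 + 0.3317 (x of 5 or more) = 0.860. This reproduces the stated 86% power.
- p = 0.10: 0.2131 × 0.0530 + 0.0710 × 0.2252 + 0.0158 × 0.6126 + 0.0028 = 0.040, within the stated 0.05.

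The sample size is correct; the issue is the endpoint definition.

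**Uncovered interval.** With readings 14 days apart and the 7-day rule applied at both, 14 − 7 = 7 days between them are not covered.

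**Timing count.** Assume one transfusion every T days. A reading is clean if the last transfusion was more than 7 days earlier, and a same-day transfusion is taken to follow the blood draw. If the last transfusion was d days before reading 1 (d = 1 to T), then at reading 2, G days later, it was d + G days before, reduced by whole cycles to lie between 1 and T. Both values must exceed 7.

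| Cycle T (days) | Gap G (days) | Timings clean at both readings |
|---|---|---|
| 14 | 14 | 7 of 14 (d = 8 to 14) |
| 12 | 14 | 3 of 12 (d = 8, 9, 10) |
| 10, 8 or 7 | 14 | none |
| 14 | 16 | 5 of 14 |
| 14 | 18 | 3 of 14 |
| 14 | 22 | 1 of 14 |

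The largest gap between consecutive biweekly visits under the ±4-day window is 14 + 4 + 4 = 22 days.

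If the 7 days were applied only at the second reading, T − 7 of T timings would pass: 7 of 14, 5 of 12, 3 of 10, 1 of 8, and none at 7 days.

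**Count criterion.** Passing the transfusion clause is not enough. Two red-cell routes remain:

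1. *Discretionary transfusion.* A non-symptomatic subject reads 10 g/dL or more at both visits and is transfused in between above the 6.6 triggers, as discretion allows.
2. *Symptomatic subject with a rise.* A rise of 2 g/dL that leaves hemoglobin below 9 g/dL needs a baseline below 9 − 2 = 7 g/dL. For example, 6.5 rising to 8.6 is a gain of 2.1, which qualifies, while 8.6 with symptoms still meets the 6.6 trigger.

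**Illustration of the effect on error.** The documents give no misclassification rate, so m is assumed. If a share m of true non-responders is counted as responders, the apparent rate is 0.10 + 0.90m.

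| m (assumed) | Apparent rate | Chance of rejecting H0 | Chance of stopping at stage 1 |
|---|---|---|---|
| 0 | 0.100 | 0.040 | 0.697 |
| 2.5% | 0.1225 | 0.082 | 0.602 |
| 5% | 0.145 | 0.143 | 0.512 |

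**The case against.** The strongest reply is that the gap is narrow once the count criterion is applied, and much of that stands.

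- **Visit-prompted transfusion.** A reader might infer that, because the visit blood count prompts the transfusion, nearly every biweekly-transfused subject passes at every visit. The documents do not support this. A reading below 7 g/dL, or below 9 g/dL with symptoms, fails the 10 g/dL route, and a reading of 10 or more triggers nothing. To be at 10 on day 8 and below 7 by day 14, hemoglobin must fall faster than (10 − 7)/6 = 0.5 g/dL per day. On a straight line, that puts it above 10 + 8 × 0.5 = 14 g/dL just after transfusion.
- **Direction of bias.** A reader might infer that the bias runs only towards success. The uncovered interval can only add responders. However, baseline may be read from 72 hours after a transfusion, so it may already contain donor cells, which makes the above-baseline route harder to meet.
- **Platelets and Evans syndrome.** Carry-over of platelets 8 or more days after transfusion is expected to be small (an assumption; the documents give no figure), and Evans subjects must meet both criteria.
- **Existing data.** Transfusion support is reviewed at each visit (Schedule of Activities, note a) and weekly requirement is a secondary endpoint, so continuing need would be visible in the results. It would still not alter the primary classification.

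The objection limits how often this can happen. It does not close the gap in the text, and both red-cell routes survive it.

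**Conclusion.** The point holds as a gap in the endpoint definition. A subject transfused about every 12 to 14 days, still dependent by the protocol's own definition, can satisfy the transfusion clause at both readings. The 7-of-14 figure is the top of the range: it needs a regular 14-day cycle and readings a whole cycle apart, and it counts timing only.

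The frequency is unknown. It depends on how long a red-cell increment persists 8 to 14 days after transfusion and on how often transfusions are given at discretion, and the documents give neither. The error rates of 0.082 and 0.143 show how sensitive a 5-of-20 rule is. A reader should not take them, or anything larger, as estimates of this trial's type I error.

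A reader might also infer that a 14-day red-cell look-back before the first reading is needed. It is not needed to close this gap: 7 clean days before the first reading plus at least 14 between readings gives at least 7 + 14 = 21 transfusion-free days, which no subject on a regular cycle of 14 days or less can meet. A longer look-back is a preference.

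This is a cheap improvement; the two-stage design itself stands.

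**What to change.** Use one identical definition in Sections 1.1, 4 and 9.3.2 that:

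1. restores the minimum 2-week spacing in 9.3.2;
2. states that the 7-day rule applies at each of the two readings;
3. requires no transfusion of the component for the enrolled lineage (red cells for anemia, platelets for thrombocytopenia, either for Evans syndrome) from the first qualifying blood draw to the second.

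If the sponsor prefers to keep the primary definition, item 3 should at minimum be prespecified as a sensitivity analysis of the primary endpoint. Settle this before responses are classified for the 11-subject futility analysis.

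This changes endpoint classification only, not transfusion care. It needs a protocol amendment with IRB approval but no new assessments. Section 6.6 asks for units, so the sponsor should confirm that transfusion dates are also captured. The reported response rate may be slightly lower. The sample size, the type I error of 0.040 and the power of 86% are unchanged provided the sponsor confirms that 10% and 35% still apply to the tighter endpoint.
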